#### Study Risks and Benefits:

The known risks of IV iron therapy are minimal infusion reactions: nausea, vomiting, chills, headache, flushing, constipation, mild arthralgia/myalgia of the chest or flank or facial flushing. All of these symptoms routinely abate after therapy, and plasma tryptase levels drawn after the reaction are always normal. The symptoms are most likely due to minor reactions to labile plasma iron released with any of the formulations. Compared to the side-effects present in the majority of people taking oral preparations, such as constipation, metallic taste, gastric cramping and thick green tenacious stool, the adverse events with IV iron are minor, infrequent and short-lasting. Another concern is anaphylaxis, it

has been reported to be very rare (0.6%) with the new IV iron formulation currently in use. IV iron is consequently moving rapidly forward in the treatment paradigm. Published evidence supports a wider and earlier role for IV iron in the management of postpartum anemia and raises the question of whether it should be frontline therapy in such condition.

## **2. Concise Summary of Project:**

This trial will be a comparative pragmatic double blinded feasibility randomized controlled trial of daily versus IV iron in anemic postpartum patients.

Two randomly assigned groups will be compared during the postpartum period:

1. **Oral Iron group:** Ferrous sulfate 325 mg (65 mg elemental iron) by mouth for a total of 6 weeks TID.

IV placebo in sodium chloride 0.9% 500mL IV infusion will be given before discharge home over 1.5 hour preceded by placebo test dose IV infusion of 100mL 0.9% sodium chloride.

2. **IV Iron group:** Low molecular weight iron dextran (infed) 1000mg in sodium chloride 0.9% 500mL IV infusion over 1.5 hour preceded by test dose 25 mg IV low molecular weight iron dextran infusion in 100mL 0.9% sodium chloride.

2.1 Oral placebo will be given by mouth for a total of 6 weeks TID.

The number of subjects studied will be 40 at UTMB, we plan to approach and consent up to 40 patients to allow for screening failures, early withdrawals, and patients lost to follow-up, and patients who must withdraw due to failure of therapy. This number was decided for the aim as a feasibility trial goal. Study to last an anticipated length of 1 year. If our sample size is not achieved by that time, we will consider the trial as not feasible at UTMB only. This trial will provide important information such as eligibility, consent, and outcomes rates on which to base feasibility and sample size calculations for a larger definitive trial, as well as how many clinical sites would be needed.

## **3. Study Procedures:**

### Patient Population

The patient population will be selected from obstetric patients who delivered at UTMB health system. This population can broadly be divided into patients cared for by one of the UTMB faculty obstetric providers and those who receive care through the Regional Maternal and Child Health Program (RMCHP). We anticipate that the majority of the patients in this study will be recruited from the RMCHP patients.

### Locations

John Sealy hospital will be our recruitment site. Research staff will be present at the location and consenting and enrolling will only occur when research staff are present.

### Research Team

The research team (or research staff) will consist of the PI, trained research coordinator, and additional staff to be trained and added to the research protocol. All members of the research team will be able to screen and consent subjects. The PI will work to ensure that the team is of sufficient size to carry out the project. Consenting and enrollment of subjects will only occur when a research team member is physically present at the study location.

## Screening

All pregnant patients who deliver in our unit undergo a laboratory screen for anemia at the first postpartum day as part of the UTMB standard of care while recovering in the hospital. Eligible patients (PPD#1 patients with a hemoglobin less than 9 g/dl) will be screened and approached while inhouse (detailed under section 8).

The anticipated procedures flow is as follows

1. Research staff will go to postpartum ward.
2. Research staff will confirm with provider that possible subjects are appropriate candidates for treatment with ferrous sulfate.
3. Research staff will approach screened patients to obtain consent from possible subjects.
4. Subjects will be randomized using a computer-generated sequential randomization log with group assignment, subject name, and medical record number.
5. After patient is consented and enrolled, the provider will be notified orders will be placed in EPIC by providers with the assistance of the research staff; and a note will be placed in the electronic chart indicating that the patient is enrolled in the study.
6. Subjects will continue to receive standard, routine postpartum care and surveillance of postpartum iron anemia.
  - a. Research staff and PI will periodically monitor surveillance data by chart review.
7. During their routine 6 weeks postpartum visit, patient's hemoglobin level will be obtained (standard of care at UTMB). If subjects have a hemoglobin level drawn before the 6 weeks visits, such as in the 3 weeks postpartum visit, we will also collect this information.
8. Research staff will conduct chart review to obtain the data points for the primary and secondary outcomes (described in section 1)

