## **5. Criteria for Inclusion of Subjects:**

- Maternal age  $\geq$  18 years and  $<$  50 years
- Delivery at UTMB
- Hemoglobin below 9 g/dl in postpartum day 1: This population has the highest risk to have complications from postpartum anemia, protracted recovery and the most to benefit from IV iron (4 studies showed benefit of IV iron at 6 weeks PP in subjects with baseline hemoglobin values ranging from 7.4 to 8.1 g/dL.)
- Singleton gestation

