## **6. Criteria for Exclusion of Subjects:**

- Enrolled in another trial that may affect outcome at the discretion of the PI
- Diagnosis of malabsorptive disorder or history of gastric bypass procedure
- Known diagnosis of anemia other than iron deficiency (thalassemia, macrocytic anemia, sickle cell, etc.)
- Significant cardiovascular disease, including but not limited to myocardial infarction or unstable angina within 6 months prior to study inclusion or current history of NYHA Class III or IV congestive heart failure
- Patient has received blood transfusion or there is a plan to transfuse
- Lactose intolerance

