## **8. Recruitment Methods and Consenting Process:**

Patients delivered at UTMB Galveston campus will be screened to identify patients with a hemoglobin below 9 g/dl in postpartum day 1 who also satisfy the other eligibility criteria. Clinical providers will be educated about the trial prior to enrollment. We plan to identify these patients by screening the charts of patients delivered in our labor and delivery unit to identify potential subjects. Information to be reviewed as part of the screening process will be hemoglobin laboratory data and relevant exclusion and inclusion history. Research staff will function as the screeners and will alert providers that their patient is a potential subject. The provider caring for that patient will then be informed of the patient's eligibility. Research staff will work with the provider to ensure that the study intervention is appropriate therapy for the patient. If the provider agrees that the study intervention is appropriate, the provider will then approach the patient to ascertain interest in participation. If the patient is interested, the provider will introduce the research staff to the patient who will then explain the study to the patient as part of the consenting process. A screening log will be used to track all subjects approached for the study. At the time of consent and randomization, the patient will be educated as to the dosing regimen as well as the routine treatment surveillance that will occur. This will be done by the research staff consenting the patient.

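### No eligibility criterion excludes a woman with a known serious reaction to iron dextran or other IV iron, and screening step 2 asks only about ferrous sulfate; the remaining checks are general and do not name the hazard

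*Combined protocol and SAP*

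**What the plan says.** Section 5 lists four inclusion criteria: age, place of delivery, haemoglobin on the first postpartum day, and "Singleton gestation". Section 6 lists six exclusions: certain other trials, malabsorption or gastric bypass, anaemia of another cause, significant cardiovascular disease, transfusion given or planned, and "Lactose intolerance".

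Step 2 of the procedures flow in section 3 (Screening) is: "Research staff will confirm with provider that possible subjects are appropriate candidates for treatment with ferrous sulfate". The opening paragraph of the same section says that eligible women "will be screened and approached while inhouse (detailed under section 8", so section 8 must be read with it. Section 8 says:

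- On training: "Clinical providers will be educated about the trial prior to enrollment".
- On the chart screen: "Information to be reviewed as part of the screening process will be hemoglobin laboratory data and relevant exclusion and inclusion history".
- On suitability: "Research staff will work with the provider to ensure that the study intervention is appropriate therapy for the patient".
- On who makes the first contact, and under what condition: "If the provider agrees that the study intervention is appropriate, the provider will then approach the patient to ascertain interest in participation".

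Under Brief Study Design and Rationale (section 1), the IV arm receives a 25 mg test dose of iron dextran and then 1000 mg. The same text gives oral iron as the local standard of care for postpartum anaemia. Study Risks and Benefits (section 1) names anaphylaxis as a concern with IV iron and puts it at 0.6%.

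**The concern.** A woman known to have reacted seriously to iron dextran or another IV iron meets every written criterion. She could be randomised to a full dose of iron dextran without any protocol deviation. Under the usual care the protocol describes, she would receive oral iron. The IV exposure, and any avoidable reaction to it, would therefore come from the trial.

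Step 2 adds to the difficulty. It asks about suitability for ferrous sulfate, which usual care may well have given her anyway, and not about the drug that the trial adds. What is at stake is patient safety; the sample size and the analysis are not affected.

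**Working it through.** No calculation in the plan bears on this point. The check is to follow a woman with a known serious IV-iron reaction through each stated step and ask whether the text would stop her.

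1. **Inclusion criteria (section 5).** Four criteria, none on drug tolerance. She passes.
2. **Exclusion criteria (section 6).** Six criteria. The only intolerance named is to lactose. The investigator's discretion appears only in the line on enrolment in another trial, so it is not a general safety exclusion. She passes. Across both lists, 4 + 6 = 10 criteria, and 0 of 10 address tolerance of IV iron.
3. **Chart screen (section 8).** It covers haemoglobin and history relevant to the listed criteria. No criterion concerns IV iron, so an earlier reaction is not among the items sought. It could be noticed by chance.
4. **Step 2 (section 3).** The question concerns ferrous sulfate. A provider could truthfully answer yes for a woman who tolerates oral iron and has reacted to IV iron.
5. **Provider agreement (section 8).** The question here is wider: whether the trial's intervention suits the patient. Section 4 counts IV as well as oral iron among the intervention drugs, so a provider educated about the trial should have IV iron in mind. This is a real safeguard, and she may well be stopped here. But it is a general judgement that does not prompt for an earlier reaction, and the provider has just been told that the woman is eligible under a list without that item.
6. **Ordering, dispensing and administration (section 3, step 5; section 4).** Providers place the orders, the investigational pharmacy dispenses, and a nurse administers. No allergy check is stated at these points, though routine practice may include one. All of them come after consent, and dispensing and administration come after randomisation.
7. **Test dose (section 1).** It is 25 mg of iron dextran, given after randomisation. For this woman it is a re-exposure and cannot replace screening by history.

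Steps 1 to 4 do not stop her as written. Step 5 may, and step 6 might. None of the seven names the hazard.

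**The case against.** The strongest reply is that section 8 already deals with this. Staff must satisfy themselves with the provider that the intervention is suitable, the woman is approached only if the provider agrees, and the intervention includes IV iron. A known serious reaction to this drug class is among the clearest reasons a provider could have to decline. Step 2 is one line in a summary flow, and the section containing it points to section 8 for detail. Clinician ordering and nurse administration follow, and the woman herself has a consent discussion.

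Most of this stands. A reader might infer from the two criteria lists that nothing prevents such a woman from being dosed. The documents do not support that: the section 8 agreement would probably catch many of them. Nor can it be said that women are never asked about iron reactions at consent, because the consent pages are not available for this review.

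A reader might also be tempted to attach a probability. At the protocol's 0.6%, with 20 of 40 women assigned IV iron (1:1 allocation), the expected number of anaphylaxis cases is 20 × 0.006 = 0.12, and the chance of at least one is 1 − 0.994^20 = 11.3%. That is the risk of a reaction among treated women in general, which the exclusion would not remove. It could stand for the chance of enrolling a woman with a known reaction only if every woman had earlier received IV iron and no provider stopped anyone. Neither is plausible when the protocol describes oral iron as standard.

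What the reply does not answer is that the safeguard depends on someone thinking of an item that the criteria, the chart screen and step 2 all leave out.

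**Conclusion.** The concern holds in a limited form. As written, a woman with known hypersensitivity or a previous serious reaction to iron dextran or other IV iron is eligible, and step 2 checks the wrong drug for the hazard that the trial introduces. The section 8 agreement and the later clinical steps reduce the chance that she is dosed, but they do not name the problem.

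The size cannot be given as a rate. The documents report neither how many women have had IV iron before nor how many of those reacted, and the number is likely low. The case rests on three things: the harm can be severe, as the protocol's own mention of anaphylaxis implies; it is preventable when the history is known; and usual care would not expose her. That makes the change a cheap improvement that should be made. It does not show that the trial is unsafe as run.

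**What to change.** Add one line to section 6: *Known hypersensitivity or previous serious reaction to iron dextran or any other IV iron.* This does the main work. The section 8 chart screen already reviews exclusion history, so it would then look for this item, and a known reaction would make the woman ineligible before consent. Extending the line beyond iron dextran to other IV iron is a clinical judgement, since the documents say nothing on cross-reactivity; the investigator should confirm it.

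Align step 2 in section 3 so that the provider confirms that possible subjects are *appropriate candidates for both oral ferrous sulfate and IV low molecular weight iron dextran*. Matching wording in section 8 is optional, because the general phrase there already takes in IV iron.

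The cost is two short text changes, with no new test or visit and no change to the planned 40 women. The downside is possibly a few fewer eligible women.

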## **4. Disposal and Administration of Drug and Placebo/Drug compliance**

The intervention drugs (IV/PO Iron and placebo) will be provided by Greenpark Compounding Pharmacy and UTMB Investigational Drug Service (IDS). The latter will receive, store and dispense the drugs for the study.

Once a qualified subject is consented and randomized, an order will be entered in Epic. The UTMB IDS will be notified to dispense the study drug according to the treatment assignment per study protocol. The assigned drug and placebo will be delivered to the nursing unit to be administered by the nurse assigned to the subject. The assigned nurse will document the administration in Epic using Medication Administration Record (MAR). Any unused study drug will be returned to IDS for documentation and disposal. Medications used in this study will not be billed to the subject or her insurance company.

The IDS will dispense the pills in a container/bottle and the subject will be given the bottle and given instructions to come to clinic at 6 weeks postpartum to see provider with bottle/container. The supplies given will be enough for total treatment of 6 weeks.

The subject will be included in the analysis by intent-to-treat once the assigned pills are dispensed from IDS and sequential number posted on the subject specific randomization form.

Drug compliance: subject will be instructed to bring pill container to all clinic visits. The provider will document number of pills in the container in order to account for compliance at best in each postpartum visit and emphasize compliance. At the end of the treatment period (6 weeks postpartum visit), the research team will collect the container and count the returned pills prior to returning it to the IDS for reconciliation within 2 weeks of receiving the bottle. Study participation will end at 6 weeks postpartum. However, if subject does not come to their scheduled postpartum visits, we will do our best to attempt to contact and retrieve drug container up to 10 weeks postpartum.

If subject misses her regular postpartum visit, we will make every effort to contact the subject by phone and enquire about the outcomes.

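### The protocol names no holder for a randomization log that pairs assignment with identity, and describes nothing that keeps it from the team that recruits, assists with orders and collects outcomes

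*Combined protocol and SAP*

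**What the plan says.** Section 2 describes a "comparative pragmatic double blinded feasibility randomized controlled trial". Masking is by double dummy. For the oral-iron arm, "IV placebo in sodium chloride 0.9% 500mL IV infusion will be given before discharge home"; for the IV-iron arm, "Oral placebo will be given by mouth for a total of 6 weeks TID".

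The randomization procedure is step 4 of the numbered Screening flow in Section 3: "Subjects will be randomized using a computer-generated sequential randomization log with group assignment, subject name, and medical record number". In step 5, after consent and enrolment, "orders will be placed in EPIC by providers with the assistance of the research staff". In step 8, "Research staff will conduct chart review to obtain the data points for the primary and secondary outcomes". Under Research Team, whose members include the principal investigator and the coordinator, "All members of the research team will be able to screen and consent subjects".

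Section 4 gives the order of events: "Once a qualified subject is consented and randomized, an order will be entered in Epic". Only then is the investigational pharmacy notified to dispense by assignment. Its stated role is to receive, store and dispense. The same section has the research team count returned pills at 6 weeks. It also brings a subject into the intention-to-treat analysis only when the pills have been dispensed and a sequential number has been entered on a subject-specific form.

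**The concern.** Concealment of upcoming assignments and blinding after assignment are separate protections. A double dummy supplies the second. It does nothing for the first, and it fails for anyone who can read a list that shows arm beside name.

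Two things are at stake. If upcoming assignments can be foreseen, the decision to approach a patient, or to complete enrolment, can depend on the arm she would get. If past assignments can be read, staff who abstract adverse effects or count pills know the arm while doing so. The protocol gives these tasks to one team and does not say how that team is kept from the list.

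**Working it through.** **The plan's own figure.** No figure in the protocol tests this point, but the sample size reproduces. Inputs from Section 13: d = 0.9592329, two-sided alpha 0.05, 80% power, 1:1 allocation, 5% loss.
- Noncentrality = d × √(n/2) = 0.9592329 × √9.5 = 2.9566 with n = 19 per group; df = 36; critical t = 2.0281.
- Power = 0.8204 at n = 19, and 0.798 at n = 18. So 19 per group, 38 in total.
- 38 / 0.95 = 40.

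Better concealment would not change any of these.

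**The relevant sections side by side.**

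| Question | What the protocol gives |
|---|---|
| Who generates the list? | Computer-generated; no person or unit named |
| Who holds it? | Not stated; the pharmacy's listed duties (Section 4) do not include it |
| When is an assignment fixed? | Before the Epic order and before the pharmacy is notified (Section 4); Section 8 treats consent and randomization as one moment, with teaching by the staff member taking consent |
| How are upcoming assignments hidden? | No envelopes, central system, pharmacy-held list or coded supplies described |
| What does Epic show? | Not stated for the order or the administration record |
| Who collects data? | Research staff, by chart review (Section 3, step 8; Section 7); the research team counts pills (Section 4) |

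**Where foreknowledge could act.**
1. *At approach.* Provider and staff judge whether the intervention suits the patient (Section 3, step 2; Section 8). Exclusions include a plan to transfuse and, at the investigator's discretion, co-enrolment in another trial (Section 6). The screening log covers those approached (Section 8), so an eligible woman who was never approached would not appear in it.
2. *Between randomization and dispensing.* Because intention-to-treat membership starts at dispensing (Section 4), a subject lost in that interval falls outside the analysis set although already assigned.
3. *At analysis.* Section 13 plans a t test or rank-sum test with no baseline adjustment, so an imbalance produced in either way would pass into the comparison.

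**Illustration only.** Suppose selection pushed the arms apart by b standard deviations with no true effect. With SD 1.2 g/dL and 19 per group, noncentrality is b × √9.5, and the two-sided 5% test rejects as follows:

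| Assumed b | Bias (b × 1.2 g/dL) | Rejection rate |
|---|---|---|
| 0.1 | 0.12 | 6.0% |
| 0.2 | 0.24 | 9.2% |
| 0.3 | 0.36 | 14.7% |
| 0.5 | 0.60 | 32.3% |

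The protocol offers no basis for choosing any row. The table shows how the test responds to a bias; it does not predict one.

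**The case against.** A reader might infer that assignments are in fact open to the staff who recruit, order and assess. The documents do not say so. Step 4 is in the passive and names no actor, while neighbouring steps name research staff. The pharmacy could hold the log. The double dummy, pharmacy dispensing, the separate password-protected enrolment log and data stored by participant ID (Section 11) all show an intent to mask. Every blinded trial also has some record linking subject to arm; its existence does not break the blind, whereas access to it would. So it is too strong to call the log incompatible with the double blind. Nor does the protocol say that the Epic entry displays the arm.

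The consequences can be overstated too. The primary outcome is a routine laboratory hemoglobin, which leaves an informed abstractor little room. The fatigue and depression scales are questionnaires, and nothing says research staff administer them. A log seen by staff would not by itself unblind a patient on double dummy. Selective approach is partly constrained, because Section 8 has the treating provider agree and make the first approach. A bias in g/dL would need an assumed baseline imbalance and an assumed slope on baseline; the documents give neither, and the entry ceiling of 9 g/dL narrows the baseline range.

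All of this stands, and it limits the point to what the protocol leaves unprotected. It does not close the gap. Intent to mask is not a concealment procedure, and the one procedure described pairs arm with name inside the ward recruitment flow, ahead of any pharmacy involvement.

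**Conclusion.** The point holds as a gap in the stated procedure, and as a cheap improvement rather than a demonstrated failure. The log pairs assignment with identity, it is used before the pharmacy is notified, and no custodian or barrier is described. Whether recruiting staff actually have access is unknown. The risk to the primary outcome runs mainly through selection, including loss between randomization and dispensing; adverse-effect abstraction and pill counts are more exposed to knowledge of the arm. The size of any bias cannot be estimated from the documents. The conclusion assumes that no separate pharmacy or randomization procedure outside the protocol already covers this. If one does, citing it would settle the matter.

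**What to change.** - **Section 3, step 4:** state that the investigational pharmacy, or another person independent of recruitment and outcome collection, generates and holds the assignment list and reveals each assignment only to the dispenser, after consent and enrolment.
- **Logs:** remove the group-assignment column from any log that research staff use; name, record number and study number are enough.
- **Section 3, step 5, and Section 4:** specify a generic blinded study-drug entry for the Epic order and the administration record.

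With assignments known only to the dispenser, a loss before dispensing could not depend on recruiting staff knowing the arm. A block scheme is optional.

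The cost is one paragraph and a pharmacy work instruction, with no change in sample size. The downside is that the list holder must be reachable at each randomization. Dispensing already requires this of the pharmacy; a different holder would need cover arranged.
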